12. STATISTICAL CONSIDERATIONS

12.1. Study Hypotheses

Primary hypothesis. Null hypothesis is that the proportion of patients with a successful outcome of WHO OM severity grades 0-2 at the post study evaluation will not differ between the two randomized intervention groups. The estimated proportion of successes from our pilot trial is 0.30 with SOC. The alternative hypothesis is that the proportion of patients with a successful outcome differs between the two groups from the SOC proportion of 0.30 by +/-0.265 or more.

Secondary objectives will test whether or not there are differences in changes in cytokines levels over time by treatment group, and in other measurements, including time to onset and duration of severe OM (greater than 2), duration and time to onset of severe OM, salivary hypofunction, average mouth and throat soreness (MTS), and quality of life and function [EORTC QLQ 30 and EORTC QLQ HN35].

12.2. Sample Size Considerations

For the primary clinical study outcome of OM severity (WHO OTS scale) at end of RT/chemoRT, for simplicity, and for conservative sample size estimation, we consider subjects with grades 0, 1, 2 OM as having a successful outcome, and with OM grade greater than 2 as a failure. Subjects who never develop or scored 1 on the WHO mucositis scale will be considered as a success if they complete the end of treatment visit. The overall study will randomize 120 subjects in four strata. Sixty-five percent of eligible participants are expected to be treated with RT alone, the remaining 35% are expected to be treated with chemoRT. Approximately 45% of participants are expected to receive Proton therapy, 55% IMRT. The expected overall success rate on RT or chemoRT is estimated as 30% with SOC. With 1:1 randomization into the 2 treatment arms, with 80% power and 2-sided alpha of 0.05, we can detect a difference in this success rate of |26.5 %| based on Fisher's exact test for proportions (exact alpha = 0.03; 60 subjects per arm across the four strata). Further, within the RT stratum with 39 subjects/intervention arm, we can detect a difference of |33.3%| and within the chemoRT stratum with 21 subjects/intervention arm, we can detect a difference of |46.7%|. Within the smallest stratum of chemoRT and Proton RT, for example, we would have 9 patients intervention group and a comparable detectable difference of |65%|. While this detectable difference is very large, there is no reason to expect heterogeneity among the strata. However, we will examine the homogeneity of the effects across the four strata using a Gail-Simon test for qualitative interaction. Unless there is a statistically significant difference (at the 0.10 level) in this test for qualitative interaction with respect to outcome and treatment effect in the four strata, results will be combined. Unless otherwise specified, all sample size calculations were performed using PASS 2014 software, NCSS, J. Hintze, Kaysville, UT. Similar sample size considerations would apply to the end of study comparison of OM grade. We note that we evaluate the primary outcome at both the end of RT/chemoRT (Visit 9/FIV), and at the end of study visits (Post-RT Visit). These two time points will be evaluated with no adjustment for multiple analyses.

For the quantitative secondary outcomes that include changes in salivary proinflammatory cytokines, and the following clinical indicators: a) duration of and time to onset of severe OM, b) salivary hypofunction, c) average mouth and throat soreness [MTS], and d) quality of life and function as measured by selected instruments [EORTC QLQ 30 and EORTC QLQ HN35]), we can detect a difference of $|.5|$ standard deviations of the difference between the two intervention groups with 60 participants/group for a single measurement at a single timepoint with 2-sided alpha of 0.05 and power of 80%. These detectable differences range from $|.6|$ standard deviations to $|1.4|$ standard deviations as the strata size ranges from 9 to 39 per intervention group.

Details for the one planned interim analysis of the primary endpoint are provided in Section 12.4 below with the fixed planned study sample size of 120 participants.

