12.3. Planned Interim Analyses

A formal interim analysis for efficacy and futility will be carried out when 50% of the participants have been accrued and would have been evaluable for the 3-month post treatment visit. With the planned accrual of 120 participants over 3.5 years, we expect this analysis to occur at approximately 2.5 years after the first patient is randomized to the study. The planned timing of this interim analysis is early enough to allow sufficient time to impact on the trial accrual within the time frame of this trial. That is, this planned interim analysis will occur while patients are still actively being randomized to treatment. Randomization of participants would not be halted during the review period. The table below provides the detectable differences and alpha and beta spending for the planned interim and final analysis. The boundaries for efficacy and for futility at the interim and final analyses are provided in Table 1 below that provides the detectable differences and p values.

Table 1. Detectable Differences and p values for Interim and Final Analyses to Detect a Difference in the Proportion of Patients OM Response of $|0.265|$ on Intervention Compared with SOC (0.30) based on z test to compare proportions (Casagrande-Pike-Smith Correction], unpooled variance estimate 2-sided $\alpha = 0.05$; power = 0.80; 60 patients/treatment group O'Brien Fleming Boundaries, Lan-DeMets Spending Function for Efficacy and Non-Binding Futility.

Table 1.

Analysis	Number of Participants	Cumulative α Spent	Efficacy Boundary		Cumulative β Spent	Futility Boundary	
			Difference Treat-SOC	p-val, z statistic		Difference Treat-SOC	p-val, z statistic
Interim	60	0.003	$ 0.39 $	≤ 0.003	0.039	$ 0.046 $	> 0.724
Final	120	0.050	$ 0.183 $	≤ 0.049	0.198	$ 0.183 $	> 0.049

[Calculations from EAST V6.4.1 Cytel, Inc.]

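### The SAP does not fix one primary visit: 12.1 tests one, 12.2 sizes on another, both are tested unadjusted, and Table 1's single 0.05 is tied to neither

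*SAP*

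**What the plan says.** - **12.1 (hypothesis).** The primary null hypothesis is that the proportion with a "successful outcome of WHO OM severity grades 0-2 at the post study evaluation will not differ between the two randomized intervention groups". The control rate comes from earlier data: "The estimated proportion of successes from our pilot trial is 0.30 with SOC". The alternative is a difference of 0.265 or more.
- **12.2 (sample size).** The calculation opens "For the primary clinical study outcome of OM severity (WHO OTS scale) at end of RT/chemoRT". It uses the same 30% and 26.5 points, with 60 per arm, Fisher's exact test, 2-sided 0.05 and 80% power. For the other visit it says only: "Similar sample size considerations would apply to the end of study comparison of OM grade". It then states that the primary outcome is evaluated at both visits, and adds "These two time points will be evaluated with no adjustment for multiple analyses".
- **End of 12.2.** The text becomes singular: "Details for the one planned interim analysis of the primary endpoint".
- **12.3 (interim).** The look takes place "when 50% of the participants have been accrued and would have been evaluable for the 3-month post treatment visit". Table 1 spends one 2-sided 0.05 (0.003 at the interim, final p ≤ 0.049) on OM response and names no visit.
- **12.4 (analysis).** Under the primary objective, a CMH test is applied at both visits.

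**The concern.** Each section is workable alone, but together they describe two primary comparisons and one alpha budget. Nothing ranks the visits, requires both to succeed, or divides alpha between them. If one visit gives p ≤ 0.049 and the other does not, the SAP does not say whether the trial is positive. At the interim it does not say whose result is held against the efficacy and futility limits. Left open until data are seen, the choice of visit can follow the result. The shared 0.30 and 0.265 do not help, because 12.1 and 12.2 attach them to different visits.

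**Working it through.** **1. The plan's own figures, for one visit.** Inputs from 12.1 and 12.2: 60 per arm, 0.30 against 0.565, 2-sided Fisher at 0.05. Full enumeration gives power 0.801 and exact alpha 0.031 at 0.30, matching the stated 80% and 0.03.

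Table 1 uses O'Brien-Fleming-type Lan-DeMets spending, α(t) = 4[1 − Φ(z₀.₉₈₇₅/√t)]. At t = 60/120 = 0.5 this is 4[1 − Φ(2.2414/0.7071)] = 4[1 − Φ(3.170)] = 0.00305. The final nominal level is then 0.0490. Both match Table 1. The arithmetic is right for a single comparison at a single visit.

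**2. If a win at either visit counts.** With no interim and independent visits, the error is 1 − 0.95² = 0.0975. For the actual design, 300,000 trials per setting were simulated with:
- looks at 30 and 60 per arm and limits p ≤ 0.003 and p ≤ 0.049 at both visits;
- success 0.30 in both arms at both visits;
- strata of 18/21/9/12 per arm (rounded from the 65/35 and 45/55 splits in 12.2), and 9/11/4/6 at the interim.

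The SAP gives no between-visit correlation, so a range is assumed.

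| Test | One visit | Corr. 0 | 0.5 | 0.8 | 0.95 |
|---|---|---|---|---|---|
| CMH, uncorrected | 0.049 | 0.096 | 0.090 | 0.077 | 0.064 |
| CMH, continuity-corrected | 0.030 | 0.059 | 0.055 | 0.048 | 0.039 |
| Fisher (used for sizing) | 0.031 | 0.062 | 0.058 | 0.050 | 0.041 |
| Unpooled z, continuity-corrected (a reading of the Table 1 test) | 0.035 | 0.068 | 0.064 | 0.055 | 0.045 |

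Section 12.4 does not say which CMH version applies. Holding the interim on one visit only changes little: in a normal approximation the either-visit error is 0.097, 0.090, 0.077 and 0.064.

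**3. If both visits must win.** Error cannot exceed the one-visit level. Power at 0.30 against 0.565 at each visit (final test at 0.05, no interim) is:

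| Test | One visit | Corr. 0 | 0.5 | 0.8 | 0.95 |
|---|---|---|---|---|---|
| Fisher | 80% | 64% | 69% | 73% | 77% |
| CMH, uncorrected | 85% | 72% | 76% | 79% | 82% |

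**4. How often the visits would disagree.** With the design effect present at both, exactly one Fisher test is significant with probability 2 × (0.801 − joint power). Joint power of 0.642, 0.689, 0.731 and 0.769 gives about 32%, 22%, 14% and 6%.

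**5. The interim, if end of RT/chemoRT is primary.** When 60 participants are evaluable at the 3-month visit, those up to three months behind them already have the earlier outcome. At uniform accrual, 120/42 = 2.86 a month, so 3 × 2.86 ≈ 9 more, and information is 69/120 = 0.575. Spending is then 4[1 − Φ(2.956)] = 0.0062, not 0.003, with limits p ≤ 0.0062 and p ≤ 0.048. For 66 to 72 participants the interim limit runs from 0.0050 to 0.0076. Keeping the Table 1 limits with 69 participants gives error 0.0497. Alpha is safe, but the look no longer follows the stated spending function.

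**The case against.** - **The interim points to the later visit.** Waiting for the 3-month visit makes most sense if that visit is tested, which would agree with 12.1. This is a fair hint. But 12.3 uses the visit only to time the look, never says it is the Post-RT Visit, and sits beside a sample size built on the other visit.
- **The lack of adjustment is declared, and inflation is not proven.** No text says that either visit suffices, and with corrected or exact tests at high correlation the error is at or near 0.05. This stands, so the error figures are conditional. Disclosure still does not supply a success rule.
- **The power loss is mixed.** With uncorrected CMH and correlation of 0.8 or more, requiring both visits gives 79% to 82%, in line with the plan. This also stands. Those figures use one final look while the error figures use two, so they should not be read as one design.
- **The accrual assumption is loose.** Uniform accrual puts the 60th randomisation at 21 months, while 12.3 expects the interim at about 30. Suppose instead that the 60th participant was randomised no later than month 30 − 3 = 27 and the rest enter steadily to month 42. The rate is then at most 60/15 = 4 a month, or 12 extra participants in three months. That is 72, the top of the range above.
- **A fixed sequence is not the only cure.** Requiring both visits or splitting alpha would also settle the matter. True, but each costs power.

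**Conclusion.** The SAP is wrong as written and must be corrected before any unblinded look. Its sections contradict each other on the primary visit, no decision rule resolves this, and Table 1 is tied to no visit. That conclusion rests on the text alone and needs no assumed correlation.

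The size of the consequence depends on the rule eventually applied. An either-visit rule gives an error of about 0.06 to 0.10 with uncorrected CMH and about 0.04 to 0.07 otherwise. A both-visits rule leaves error controlled but lowers Fisher power to between 64% and 77%. These ranges assume between-visit correlations of 0 to 0.95, the 0.30 control rate at both visits, the rounded strata, and (for power) the 26.5-point effect at both visits. *Post study evaluation* is read as the end of study (Post-RT) visit.

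**What to change.** The sponsor names one primary visit and uses it in 12.1, 12.2, 12.3 and 12.4. Replace the no-adjustment sentence in 12.2 with:

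> The other visit is secondary. It is tested only if the primary visit is significant, at the same look and the same Table 1 p-value limit (fixed sequence).

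State in 12.3 that the Table 1 boundaries apply only to the named visit. Then:

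- **If end of RT/chemoRT is named,** either limit the interim to the 60 participants evaluable at the 3-month visit, which keeps Table 1, or recompute the efficacy and futility limits at the actual information fraction. In the second case the other visit keeps its Table 1 limits, because the recomputed ones applied to it at 60/120 would give error 0.0506.
- **If the Post-RT Visit is named,** say whether it is the 3-month visit, and confirm that the 0.30 control rate and the 12.2 sizing hold there.

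**Cost.** This is a change of SAP wording with 120 participants kept, provided the 0.30 rate and the sizing hold at the named visit; otherwise the detectable difference or the sample size must be revisited. Error stays at or below 0.05 for any correlation, and Fisher power at the named visit stays 80.1%. Splitting alpha at 0.025 per visit would instead cut power to 69.5%, or raise the detectable difference from 26.5 to about 29.5 points (power 0.799).

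There are three drawbacks. The other visit cannot be claimed if the primary visit fails. If the trial stops at the interim, the other visit is tested at p ≤ 0.003 with 30 per arm, where its Fisher power taken alone is about 12% for 0.30 against 0.565. Limiting the interim to 60 participants leaves about 9 others out of that look under uniform accrual.

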12.3. Planned Interim Analyses

A formal interim analysis for efficacy and futility will be carried out when 50% of the participants have been accrued and would have been evaluable for the 3-month post treatment visit. With the planned accrual of 120 participants over 3.5 years, we expect this analysis to occur at approximately 2.5 years after the first patient is randomized to the study. The planned timing of this interim analysis is early enough to allow sufficient time to impact on the trial accrual within the time frame of this trial. That is, this planned interim analysis will occur while patients are still actively being randomized to treatment. Randomization of participants would not be halted during the review period. The table below provides the detectable differences and alpha and beta spending for the planned interim and final analysis. The boundaries for efficacy and for futility at the interim and final analyses are provided in Table 1 below that provides the detectable differences and p values.

Table 1. Detectable Differences and p values for Interim and Final Analyses to Detect a Difference in the Proportion of Patients OM Response of $|0.265|$ on Intervention Compared with SOC (0.30) based on z test to compare proportions (Casagrande-Pike-Smith Correction], unpooled variance estimate 2-sided $\alpha = 0.05$; power = 0.80; 60 patients/treatment group O'Brien Fleming Boundaries, Lan-DeMets Spending Function for Efficacy and Non-Binding Futility.

Table 1.

Analysis	Number of Participants	Cumulative α Spent	Efficacy Boundary		Cumulative β Spent	Futility Boundary	
			Difference Treat-SOC	p-val, z statistic		Difference Treat-SOC	p-val, z statistic
Interim	60	0.003	$ 0.39 $	≤ 0.003	0.039	$ 0.046 $	> 0.724
Final	120	0.050	$ 0.183 $	≤ 0.049	0.198	$ 0.183 $	> 0.049

[Calculations from EAST V6.4.1 Cytel, Inc.]

12.3.1. Safety Review

SAEs and related AEs will be summarized by treatment group, strata, visit and body system for all participants who received the intervention. Safety and toxicity will be

summarized to compare the distributions of incidence and severity of adverse events on the two intervention groups within each treatment stratum. Frequency distributions and time to event analyses (Kaplan-Meier curves) will be used to summarize the major events of interest.

12.4. Analysis Plan

Distributions of subject and disease characteristics will be summarized by randomized intervention group (and within strata by intervention group) using descriptive statistics and graphical displays (e.g. boxplots for continuous measurements and frequency displays and contingency tables for ordinal and categorical measurements). These summaries will be provided at baseline and at each study visit, including the end of study visit (Post-RT Visit). Similar descriptive analyses will be provided for all secondary outcomes as well (changes in salivary proinflammatory cytokines, and the following clinical indicators: a) duration of and time to onset of severe OM, b) salivary hypofunction, c) average mouth and throat soreness [MTS], and d) quality of life and function as measured by selected instruments [EORTC QLQ 30 and EORTC QLQ HN35]). The focus will be to identify potential heterogeneity and imbalance of randomization into the study intervention groups.

Primary Objective. The analyses of the primary endpoint will be carried out on the binary OM severity (WHO OTS 0-2, 2-4) at the end of RT/chemoRT and at the end of study using a Cochran Mantel Haenszel test to adjust for strata if there is no evidence of heterogeneity of treatment effect. If there is heterogeneity, results will be examined separately within strata. Individual trajectories of OM severity by visit will be displayed.

Additional analyses of changes over time in OM severity (with ordinal classes) will be examined using mixed effects regression models for subject specific models that require only that data be missing at random [see for example; Applied Longitudinal Data Analysis,³⁵ or General Estimating Equation (GEE) population average models that require data be missing completely at random.³⁶ These approaches take into account repeated observations, missing data, and dropouts and loss to follow up among the subjects.

Effects of dropouts. Crossovers from intervention to standard of care group and noncompliance. The assumptions of these methods will be evaluated by comparing those subjects who dropout over time with those who do not with respect to baseline, diseases, and treatment characteristics to identify potential differential dropout rates by intervention group, stratification variables, and other factors. Further sensitivity analyses will be conducted to evaluate the effects of dropout rates that may be different between intervention and control group; crossover from intervention to control group; noncompliance on intervention and SOC arms, and missing outcome and covariate data.

Adjustments for covariates. Analyses will incorporate adjustments for baseline variables (e.g. age, gender, cancer diagnosis, tumor location, RT treatment plan and modality, RT dose and targeted sites within the oral cavity) including dental health status and other factors that may impact outcome based on the analyses that compare baseline variables between the two treatment groups. Those variables that are clinically

important or that differ between the two treatment groups at baseline will be considered in these supportive analyses.

Secondary Objectives. Similar methods will be employed for the analyses of the secondary outcomes that include comparisons of changes in cytokine levels over time by treatment intervention and comparisons of changes: a) duration of and time to onset of severe OM, b) xerostomia, & c) average mouth and throat soreness (i.e. other clinical effects of the intervention), quality of life assessments, cytokines, etc.; that are evaluated over time in this study.

WHO Severity compared with CTCAE score. Data will be summarized using contingency tables for these pairwise measurements. The association between the two grading systems will be examined using nonparametric McNemar chi square tests for symmetry.

Cytokine Analysis. The focus of the analyses of cytokines is to examine the effects of the intervention compared to the control group on OM response that incorporates all the various cytokines measured over time. The strategy for the development of these prediction models for OM response will include logistic regression models (and mixed effect regression models) calibrated with cross validation or penalized logistic regression models such as LASSO,³⁷ and other methods³⁸ to identify salivary cytokines that, individually or jointly, may play a role, in addition to intervention assignment, stratification factors, and patient characteristics, in the development of OM and the severity of OM over time. The distributions of each of the cytokines will be summarized within intervention groups at baseline and over time with summary statistics and graphical displays. Bivariate scatterplots and pairwise correlation coefficients will be estimated. Preliminary analysis will compare the distributions of individual cytokines by treatment group using 2-sample 2-sided t-tests (with suitable transformation of levels if required). With a false discovery rate of 10%, and a power of 80% for each test, we can detect a true difference in cytokine level of at least 0.5 (with estimated within group standard deviations of 1.0). For a single test, the individual test alpha is 0.074; the probability of detecting all 5 tests where the true mean difference in expression > 0.5, is 0.33.

The analysis approaches described above incorporate biomarkers, demographic and clinical predictors (and potential interactions) may increase both sensitivity and specificity in OM prediction or classification accuracy. The resulting models will be evaluated using Receiver Operating Characteristic (ROC) curves and estimating increases in AUC or other appropriate statistical measures of improvement in classification. An optimal cut-off value can be selected using cross-validation by optimizing the Youden index of the ROC analysis.³⁸ Sample size determination for diagnostic accuracy studies involving binormal ROC curve indices. Additional approaches to the development of prediction models will also be considered. Results would require validation in an independent study.

Exploratory Analysis. Progression free survival and overall survival will be plotted using Kaplan Meier curves by treatment group and randomization strata. Median times to failure will be estimated along with 95% confidence intervals if there are sufficient numbers of events.

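### The repeated clinical secondary outcomes are to be compared as changes, with no main model fixed to include the outcome's own baseline value or both stratification factors, and the SD behind the 0.5 SD sensitivity figure is not defined

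*SAP*

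**What the plan says.** **Sensitivity statement (SAP 12.2).** For the quantitative secondary outcomes the SAP states: "we can detect a difference of $|.5|$ standard deviations of the difference between the two intervention groups with 60 participants/group", and this is "for a single measurement at a single timepoint with 2-sided alpha of 0.05 and power of 80" per cent. The outcomes covered are introduced by "For the quantitative secondary outcomes that include changes in salivary proinflammatory cytokines" and go on to duration of and time to onset of severe oral mucositis (OM), salivary hypofunction, mouth and throat soreness, and quality of life.

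**Analysis (SAP 12.4, Secondary Objectives).** The secondary outcomes are to be analysed by methods similar to those for the primary, as "comparisons of changes in cytokine levels over time by treatment intervention and comparisons of changes" in the clinical outcomes. The methods pointed back to are a Cochran-Mantel-Haenszel test adjusted for strata, written for the binary OM endpoint, and mixed-effects or GEE models for ordinal OM severity over time. No terms are listed for those models.

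**Covariates (SAP 12.4, Adjustments for covariates).** The baseline variables are given as examples, among them "RT treatment plan and modality, RT dose and targeted sites within the oral cavity". The outcome's own baseline value and chemotherapy are not named. Variables are considered if they are clinically important or if they differ between arms at baseline, and the analyses that use them are called supportive.

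**Data available.** The opening of 12.4 summarises the secondary outcomes at baseline and at each visit, so the baseline values will exist.

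**The concern.** Two things are left open that interact.

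First, an analyst could subtract baseline from follow-up, compare the arms without further terms, and be within the SAP. Subtracting baseline forces a coefficient of 1 on the baseline value, whereas adjustment estimates it. When baseline predicts follow-up weakly, subtraction adds noise. A weak correlation is plausible here, because baseline precedes radiation injury. Choosing covariates by observed imbalance does not repair this: the choice depends on the data and does not ensure that the most prognostic variable, usually the outcome's own baseline, is included.

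Second, the 0.5 SD figure can be read against the planned analysis only if one knows whether the SD is of a level at one visit or of a change. The SAP does not say, and it gives no correlation to convert one into the other.

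At stake is avoidable loss of sensitivity on the patient-reported and salivary outcomes, together with room to choose the model after the data are seen. The primary endpoint and the sample size of 120 are not affected.

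**Working it through.** **Inputs from the SAP (12.2).** 60 per arm, 1:1 allocation, two-sided alpha 0.05, power 80%, stated detectable difference 0.5 SD.

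**Assumed, because the SAP gives no value.** r = correlation of baseline with follow-up; k = baseline SD divided by follow-up SD; share of outcome variance explained by the strata.

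**Step 1: reproduce the stated figure.** Two-sample comparison of means:
- Normal approximation: (1.960 + 0.842) × sqrt(2/60) = 0.511 SD.
- Noncentral t: 0.516 SD.
- Power at exactly 0.5 SD: 78.2% (normal) or 77.5% (t).
- Same t method at 39 and 9 per arm: 0.64 and 1.41 SD, against the SAP's 0.6 and 1.4.

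The SAP's figures are therefore rounded two-sample results in SDs of whatever variable is analysed.

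**Step 2: residual SD under each analysis, with the follow-up SD set to 1.**
- Raw change: variance = 1 + k² − 2kr. With k = 1 this is 2(1 − r).
- Baseline-adjusted: variance = 1 − r².
- Difference between the two: (1 + k² − 2kr) − (1 − r²) = (k − r)², which is never negative.

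So in large samples the raw change is never more efficient, and it ties only when r = k.

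**Step 3: detectable difference at 80% power, in SDs of the follow-up level** (0.516 × residual SD), equal SDs (k = 1):

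| r | Raw change | Baseline-adjusted |
|---|---|---|
| 0.2 | 0.516 × 1.265 = 0.65 | 0.516 × 0.980 = 0.51 |
| 0.3 | 0.516 × 1.183 = 0.61 | 0.516 × 0.954 = 0.49 |
| 0.5 | 0.516 × 1.000 = 0.52 | 0.516 × 0.866 = 0.45 |
| 0.7 | 0.516 × 0.775 = 0.40 | 0.516 × 0.714 = 0.37 |

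If the 0.5 SD is of a level, a raw change analysis with equal SDs meets it only when 2(1 − r) ≤ 1, that is, when r is at least about 0.5.

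**Step 4: a smaller baseline SD.** With k = 0.5, chosen for illustration:
- r = 0.2: change variance = 1 + 0.25 − 0.20 = 1.05, SD 1.025, detectable 0.53, against 0.51 adjusted.
- r = 0.3: change variance = 1 + 0.25 − 0.30 = 0.95, SD 0.975, detectable 0.50, against 0.49 adjusted.

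The break-even against the stated figure moves from r = 0.5 to r = k/2 = 0.25.

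**Step 5: stratification factors.** If the strata explain an assumed 5%, 10% or 20% of outcome variance, adjusting for them brings the detectable difference from 0.516 to 0.516 × sqrt(1 − R²) = 0.50, 0.49 or 0.46 SD.

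**The case against.** **The SAP does not prescribe an unadjusted analysis.** A reader might infer from the wording on changes that baseline and strata will be ignored. The text does not support that. The secondary outcomes inherit methods that include a strata-adjusted test and longitudinal models. The covariates are examples, and the wording leaves room for other factors that may affect outcome. The item on RT plan and modality may well cover proton versus IMRT. The same sentence applies the word changes to duration of and time to onset of severe OM, which have no baseline to subtract, so the word may be loose usage for trajectories over visits. All of this stands. What remains is that the inherited test is for a binary endpoint, the inherited models list no terms, and adjustment is only supportive.

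**Section 12.2 does not say that 0.5 SD is of a level.** A reader might infer that the sensitivity statement contradicts the analysis. It need not. The statement speaks of SDs of the difference, and its outcome list begins with changes in cytokines. If the SD is that of the change, 0.5 SD with 60 per arm is correct as it stands. The single-measurement wording leans towards a level, as does the cytokine subsection of 12.4, which works with a difference in level, but neither settles it for the clinical outcomes.

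**The size of the loss is assumed.** No r, SD or strata effect comes from the SAP. A reader might infer that these outcomes are underpowered. That would need r below about 0.5 with similar SDs at both visits. The argument that makes low r plausible, a baseline taken before injury, also makes a smaller baseline SD plausible, and then the loss nearly disappears. This stands as a limit on the magnitude. It does not touch the direction, since the excess variance (k − r)² cannot be negative.

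**Conclusion.** The point holds as one of model specification. For mouth and throat soreness, salivary function and quality of life, the SAP fixes no main analysis that includes the outcome's own baseline value and both stratification factors, and it permits a raw change comparison that is at best equal to the adjusted one in large samples.

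The cost depends on quantities the SAP does not give. With equal SDs, the detectable difference under raw change exceeds the adjusted one by 0.14 SD at r = 0.2, 0.07 at r = 0.5 and 0.03 at r = 0.7. With half the SD at baseline and r = 0.2, it exceeds it by about 0.02. Whether the stated 0.5 SD is missed cannot be settled until its SD is defined.

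The point does not apply to duration of or time to onset of severe OM, nor to the preliminary cytokine t-tests. It is a worthwhile, inexpensive improvement to the secondary analyses, and it is no challenge to the primary analysis.

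**What to change.** In SAP 12.4, for mouth and throat soreness, salivary function and the quality-of-life scales:

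- Make the main analysis a mixed model of the post-baseline values, with the outcome's baseline value and both stratification factors (chemoRT versus RT alone, proton versus IMRT) as prespecified terms. A longitudinal model constrained to equal baseline means, with the same factors, is an acceptable alternative.
- Keep raw changes for description.
- Do not let observed baseline imbalance decide which terms enter the main model; leave any further covariates to the supportive analyses.

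Include the same two stratification factors in the longitudinal OM severity models.

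In SAP 12.2, state whether the 0.5 SD is the within-group SD of a follow-up level or of a change. If it is of a change, give the assumed correlation so that the figure can be put on the scale of the measurement.

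The cost is SAP wording and a few degrees of freedom. The data are already planned, and the sample size does not change.
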